Data access for research

TROP-RISK STUDY dataset

All analyses for the TROP-RISK STRUDY will be completed on fully de-identified data. This includes further de-identification to remove dates.

A designated clinical researcher ([name]) will freeze a copy of the database on 1st April 2017, so a static dataset can be used for analysis. This will be retained separately from the live database to allow reproducible analyses.

The study dataset will comprise all patients who had a troponin measured at each of the five academic centres between 2010 (2008 for University College Hospital) and 2017.

Dates will be converted to delta dates, with date zero being the date of the first troponin test. All further dates are provided as number of days from date zero. Age will be provided in years, at the time of the first troponin test.

Date of death will be converted to the number of days since date zero. All patients will be retrospectively followed up, using routinely collected data on the NHS Spine Application, Summary Care Record, until death or censoring on 1st April 2017.

Data elements

The database model will include 156 data points, grouped into demographics, emergency department attendance and inpatient episodes, biochemistry, diagnosis, angiography, revascularization, echocardiography and mortality. Diagnostic data will be based on International Statistical Classification of Diseases and Related Health Problems (ICD) discharge codes.

Outcomes

Primary outcome

The primary outcome will be all-cause mortality. The nature if the data sources means that this is the outcome that will be available and it will be available with high fidelity.

Secondary outcomes

The secondary outcomes will be:

- Acute coronary syndrome (ACS) diagnosis (unstable angina, non-ST segment elevation myocardial infarction (NSTEMI), ST-segment elevation myocardial infarction (STEMI))
- Non-ACS diagnosis
- Angiography
- Revascularisation (coronary artery bypass grafting CABG), percutaneous coronary intervention (PCI))

Statistical Methods

Baseline data

Baseline and demographic characteristics will be summarised by standard descriptive summaries:

- means (standard deviation) for continuous variables which are normally distributed
- median (interquartile range) for continuous variables which are not normally distributed
- number (percentage) for categorical variables

Age distribution

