The age distribution of patients who have a troponin measured will be compared with that of the general population using the World Health Organisation (WHO) population estimates for the UK.

Troponin data

Assay performance

Each Trust measures either troponin I or T using either contemporary or high-sensitivity assays. These tests yield results in different measurable ranges with unique cut-off points for the 99th percentile of the upper limit of normal (ULN). A summary table of the performance of each assay will be assembled.

Handling of troponin data

The study dataset will comprise all patients who have had a troponin measured at each of the five academic centres between 2010 (2008 for University College Hospital) and 1st April 2017.

In clinical practice, troponin levels are frequently dichotomised into “positive” (meaning above ULN) or “negative”. Troponin levels may have a progressive relationship with prognosis, too, but the shape of this relationship is not known across the full spectrum of values and making the assumption of a linear relationship of mortality with troponin (or log troponin) may not be secure.

For these reasons, we will treat the data in two ways.

1. We will dichotomise the peak troponin level as being either positive or negative based on the ULN for each troponin assay. This makes no assumption of the shape of the relationship.
2. To standardise the many troponin assays, we will scale the results using the ratio of the observed troponin value divided by the ULN for that particular troponin assay. For example, a patient with a troponin value of 96 using an assay which has an ULN of 40 would have a scaled result of $96/40 = 2.4 \text{ xULN}$.

In some hospitals and some assays, troponin values above a certain level are systematically reported as “more than X”. According to what the hospitals have reported so far, the threshold at which the system gives results like this is in all cases very high. In no case does this truncation of results occur below 10,000 xULN. We therefore plan to set the uppermost band to be “>10,000 x ULN”. This ensures that the unavailability of an explicit value does not affect the troponin band into which any result is allocated.

Similarly, no hospital has reported truncating lower values of troponin at a threshold that is higher than $\frac{1}{2} \text{ xULN}$. Therefore, we plan for the lowermost band to be “< $\frac{1}{2} \text{ xULN}$ ”.

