Troponin has a marked positive skew. Therefore, we plan for the bands to be spaced not arithmetically but exponentially, with narrow spacing nearer low values, where there is a higher frequency density of troponin values.

Adopting this approach for analysis has the following advantages:

1. It allows the shape of the relationship to be explored without making assumptions about the shape in advance.
2. It allows values documented in the hospital databases as “less than X” or “more than X” to be used correctly in the analysis rather than omitted or have imputed values.
3. The resulting display of the mortality relationship should be easily interpreted and applied by clinicians.

All analyses on troponin will be performed using the peak troponin level. For patients who have a single troponin measurement, the peak troponin will be based on this measurement. In the remainder of the patients who have more than one

troponin test in the same hospital episode, the peak troponin value will be defined as the highest of all measurements.

Relationship between troponin positivity, age and mortality

To assess the association of dichotomous troponin level (above ULN or not) with all-cause mortality, Cox proportional hazards regression modelling will be used. Hazard ratios will be determined for the following age groups: 18-29, 30-39, 40-49, 50-59, 60-69, 70-79, 80-89 and 90+ years. We will also stratify the hazard ratios for troponin positive versus negative groups across these age groups by troponin assay (contemporary versus high-sensitivity troponin assay).

The Kaplan-Meier method will be used to calculate and display cumulative mortality, with positive and negative troponin bands compared using the log-rank statistic.

Relationship between troponin level and mortality

The main analysis of the association of progressively higher troponins with all-cause mortality will be performed without making assumptions about the shape of the relationship, i.e. with Cox proportional hazards regression modelling.

The Kaplan-Meier method will be used to calculate and display cumulative mortality, with troponin bands compared using the log-rank statistic. The results will be stratified according to ACS diagnosis and revascularisation status.

ACS diagnosis

The ICD-10 codes in Table 2 will be used to indicate an ACS diagnosis.

ICD-10 Code	Category
I20.0	Unstable angina
I21.0	Acute transmural myocardial infarction of anterior wall

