I21.1	Acute transmural myocardial infarction of inferior wall
I21.2	Acute transmural myocardial infarction of other sites
I21.3	Acute transmural myocardial infarction of unspecified site
I21.4	Acute subendocardial myocardial infarction
I21.9	Acute myocardial infarction, unspecified
I22.0	Subsequent myocardial infarction of anterior wall
I22.1	Subsequent myocardial infarction of inferior wall
I22.8	Subsequent myocardial infarction of other sites
I22.9	Subsequent myocardial infarction of unspecified site
I24.8	Other forms of acute ischaemic heart disease
I24.9	Acute ischaemic heart disease, unspecified

Table 2. ICD-10 codes used to indicate an ACS diagnosis

Revascularisation status

Acute revascularisation will be defined as having PCI or CABG in the time window between 48 hours before and 3 months after the first troponin measurement. This will account for patients who had revascularisation, in particular PCI, as an

emergency prior to their first troponin blood test and to capture revascularisation, in particular CABG, performed as an outpatient following their index admission.

Statistical package

Statistical analyses will be performed using SPSS software version 24 (SPSS Inc., Chicago, Illinois, United States) and the results verified by replicate analysis using R 3.3.2 statistical package (the R Core Team, Vienna, Austria).

Statistical significance

All hypothesis tests will be 2-tailed. A p-value of <0.05 will be considered statistically significant. No correction will be implemented for multiple testing.

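### The 3-month revascularisation window is still open at the 1 April 2017 freeze for patients first tested in the last quarter, so some of their later procedures are missed

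*Combined protocol and SAP*

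**What the plan says.** All the relevant text is in the combined protocol and SAP.

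- **Window.** Revascularisation status defines acute revascularisation as "having PCI or CABG in the time window between 48 hours before and 3 months after the first troponin measurement". The post-test limb is there partly "to capture revascularisation, in particular CABG, performed as an outpatient following their index admission".
- **Entry.** Handling of troponin data takes in everyone with a troponin measured "between 2010 (2008 for University College Hospital) and 1st April 2017". The TROP-RISK STUDY dataset section gives the same period as "between 2010 (2008 for University College Hospital) and 2017", with no closing day.
- **Freeze and censoring.** The TROP-RISK STUDY dataset section says that a researcher "will freeze a copy of the database on 1st April 2017, so a static dataset can be used for analysis", and that patients are followed "until death or censoring on 1st April 2017".
- **Use.** Relationship between troponin level and mortality states: "The results will be stratified according to ACS diagnosis and revascularisation status". Secondary outcomes also lists revascularisation, with no time window and no specified analysis.

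The plan sets no earlier entry cut-off for the revascularisation analyses, no later data cut for procedures, no minimum follow-up, and no rule for a window that is incomplete at the freeze.

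**The concern.** The status is yes or no, and it is settled by what happens over 3 months. A patient first tested late in the entry period has only part of that time inside the static copy; one tested on 31 March 2017 has a single day. A procedure after the freeze cannot appear in the data, so under the definition as written the patient falls in the non-revascularised stratum. The plan does not say this in words. It follows from a two-valued definition applied to a frozen dataset.

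The same rule then gives different answers by calendar date alone. A patient tested in 2015 who has CABG on day 60 is revascularised. An identical patient tested in February 2017, alive at the freeze, is not. The procedures lost are the later ones, which the 3-month limb was written to catch. At stake are the consistency of the two strata and the count of procedures in the last quarter of entry. This is a separate matter from immortal time and from the tracing of deaths.

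**Working it through.** The plan gives no sample size, event count or procedure rate, so there is no figure of its own to reproduce. The check is date arithmetic plus labelled assumptions.

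**1. Who has an incomplete window.** Entry, freeze and censoring all end on 1 April 2017, and the window is 3 months. A first troponin after 1 January 2017 leaves the window open. From 1 January to 1 April 2017 is 90 days. With even entry over those days, the mean window time lost is 90/2 = 45 days.

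**2. Share of entrants (assumption: even accrual).** Share = 90 / days in the entry period. The plan gives only the starting year, so both ends of that year are shown.

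| Entry starts | Days to 1 April 2017 | Share |
|---|---|---|
| 1 January 2010 | 2,647 | 3.4% |
| 31 December 2010 | 2,283 | 3.9% |
| 1 January 2008 | 3,378 | 2.7% |
| 31 December 2008 | 3,013 | 3.0% |

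With five Trusts of equal size, four starting in January 2010 and one in January 2008, the share is (5 × 90) / (4 × 2,647 + 3,378) = 450/13,966 = 3.2%. If the accrual rate instead rose linearly threefold over the period, the share would be about 5.0% (2010 start) or 4.0% (2008 start).

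**3. Which late entrants are misclassified.**

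- Procedure before the freeze: recorded, so classed correctly.
- Died before the freeze: status is final, so classed correctly.
- Alive at the freeze, with no procedure later in the window: classed correctly.
- Alive at the freeze, with a procedure after it but inside the 3 months: counted as not revascularised. This is the only group affected.

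**4. Share of late entrants' in-window procedures that is missed.** The plan gives no timing, so two assumed shapes are used.

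(a) A share *e* of procedures occurs in the first days and the rest spread evenly over 3 months. Missed = (1 − e) × 0.5, which is 5%, 15% and 25% for e = 90%, 70% and 50%.

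(b) Time to procedure is exponential with mean *m* days, truncated at 90. Averaged over even entry, missed = m/90 − 1/(exp(90/m) − 1). The last column multiplies by 90/2,647, taking the procedure rate as constant over calendar time.

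| m (days) | Missed among late entrants | Share of all in-window procedures |
|---|---|---|
| 3 | 3.3% | 0.11% |
| 7 | 7.8% | 0.26% |
| 14 | 15.4% | 0.52% |
| 30 | 28.1% | 0.96% |
| 60 | 37.9% | 1.29% |

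Shape (a) gives 5% × 3.4% = 0.17% up to 25% × 3.4% = 0.85%, inside the same range. With threefold growth in accrual, the top of the range would be 37.9% × 5.0% = 1.9%.

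**5. Effect on the mortality curves.** Censoring and freeze share a date, so a procedure missed because of the freeze also falls after censoring. Every day that a misclassified patient contributes is before the procedure, and no survival after a procedure enters the wrong stratum. Under even accrual and ignoring deaths, all late entrants together supply (90 × 45) / (2,647 × 90) = 1.7% of the potential person-time in the first 90 days and none after that. Misclassified patients are a fraction of this.

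**The case against.** The strongest reply is that nothing of consequence is wrong. Affected patients were truly unrevascularised on every day observed, each has under 90 days of follow-up, and 0.1% to 1.3% of procedures could not plausibly change a stratified Kaplan-Meier display. The timing and accrual inputs also come from outside the documents. On the mortality curves this stands. It does not remove the inconsistency: the plan groups patients by the whole window and not by status to date, so like patients are grouped differently according to when they were tested.

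Three stronger readings are tempting, and the documents support none of them.

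- A reader might infer that late entrants as a group are put in the non-revascularised stratum, or that the definition cannot be applied to them. Most can be classed, and only the one group identified in the working is wrong.
- A reader might infer that the stratified mortality results are materially biased. The shared freeze and censoring date rules out misplaced survival after a procedure.
- A reader might take it as stated that the secondary outcome is under-counted. The 3-month window appears only under Revascularisation status, for acute revascularisation. Its use for the secondary outcome is an inference.

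It is also fair to say that excluding all late entrants removes many who are correctly classed. A written rule for incomplete windows, or procedure capture extended 3 months past the last entry, would also close the gap.

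**Conclusion.** The point holds as a minor edge effect. Some late-entrant survivors are placed in the wrong stratum by calendar date alone, and the plan has no rule for them. The size, 0.1% to 1.3% of in-window procedures, rests on even accrual from January 2010, a constant procedure rate and an assumed mean time to procedure of 3 to 60 days. The existence of the gap rests on none of these, only on the plan's own dates. The practical consequence is chiefly a low count of procedures for the last quarter, conditional on how the secondary outcome is defined. The primary analysis of all-cause mortality by troponin is untouched. Sites submit data quarterly (Database management), so the last quarter could be less complete still, but the lag is not given and no figure can be put on it.

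**What to change.** Add one sentence under Revascularisation status: results stratified by revascularisation, and any 3-month revascularisation proportion, include only patients whose first troponin was on or before 31 December 2016. The window of the last patient included then closes on 31 March 2017, before the freeze. All patients stay in the overall mortality analyses. The plan should also say whether the 3-month window applies to the secondary outcome.

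The flag must be set from the calendar date, before dates are converted to days from first troponin as the TROP-RISK STUDY dataset section requires, since analysts may not see calendar dates afterwards. It must not be replaced by a filter on observed follow-up below 90 days, which would drop early deaths from every year and bias mortality.

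The cost is one date filter and one sentence. About 3% of patients, each with under 3 months of follow-up, leave these analyses, and the stratified population differs slightly from the overall one. The restriction does not cure any submission lag at the freeze.
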